10.1.3 Description of adverse events

When recording an AE, the investigator should use the overall diagnosis or syndrome using standard medical terminology, rather than recording individual symptoms or signs. The eCRF and source documents should be consistent. Any discrepancies between the subject's own words

on his/her own records (eg, diary card) and the corresponding medical terminology should be clarified in the source documentation.

Details for completion of the Adverse Event eCRF (including judgment of relationship to study drug) are described in the eCRF Completion Guidelines.

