10.6.1 Liver function tests and evaluation of PDILI

The PDILI IMP discontinuation criteria for this study are provided in Section 10.6.1.2, with the accompanying required follow-up investigation and monitoring detailed below. All PDILI events must be reported as an AE and reported to the study site and sponsor within 24 hours of learning of their occurrence. Any PDILI event that meets the criterion for potential Hy’s Law must be reported as an AE of special interest (see Section 10.3), and, if applicable, also reported as an SAE (see Section 10.2).

Evaluation of PDILI consists of the diagnostic testing and continued monitoring included in Table 10–3 (specific tests dependent on laboratory results and corresponding symptoms) and consultation with a local hepatologist (if applicable; discussed in Section 10.6.1.1). The local

hepatologist is the expert usually consulted by the treating physician for assessment and management of potential hepatic disease. This would usually be a hepatologist, but may be a gastroenterologist. Additional investigation and monitoring may be required and adapted based on the diagnosis after the cause of the liver injury/abnormality is confirmed (details in Section 10.6.1.4).

The results of all monitoring, including laboratory testing and other testing, should be made available to the study site and sponsor.

All initial tests resulting in abnormal hepatic laboratory values need to be repeated, but appropriate medical action must not be delayed waiting for the repeat result.

If tests are done locally for more rapid results, a concurrent sample should also be sent to the central laboratory whenever possible. Medical care decisions are to be made initially using the most rapidly available results and a conservative approach must be taken if the results from the 2 laboratory tests are significantly different. Data from the local and central laboratory are to be recorded on the applicable eCRF pages.

When IMP is discontinued, all concomitant medications and herbal supplements that are not medically necessary should also be discontinued. In these cases, the investigator should also consider dose reduction for medically necessary concomitant medication and consider changing any medically required concomitant medication known to be hepatotoxic to a suitable alternative.

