10.6.1 Liver function tests

Refer to Section 6.3 for LFT withdrawal criteria.

Transaminases (AST, ALT, or both) $\geq 3 \times \text{ULN}$ but $< 5 \times \text{ULN}$, in the presence of total bilirubin $\geq 2 \times \text{ULN}$, or transaminases (AST, ALT, or both) $\geq 5 \times \text{ULN}$ will result in immediate discontinuation of study medication and withdrawal of the subject from the study. The LFTs will be repeated as soon as possible, and in no case more than 1 week later.

Transaminases (AST, ALT, or both) $\geq 3 \times \text{ULN}$ to $< 5 \times \text{ULN}$, in the presence of normal total bilirubin, will be repeated within a few days. If the repeat testing confirms the abnormality (ie, transaminases are $\geq 3 \times \text{ULN}$ to $< 5 \times \text{ULN}$ with normal bilirubin), then weekly monitoring of LFTs should continue until resolved (ie, $< 3 \times \text{ULN}$ or stable condition). The investigator is to decide whether or not to stop the study medication.

In all cases of transaminases (AST, ALT, or both) $\geq 3 \times \text{ULN}$, testing for hepatitis A, B, and C will be done.

Referral to a specialist (ie, hepatologist or gastroenterologist) is at the discretion of the investigator. This is recommended especially if the transaminase abnormalities $> 3 \times \text{ULN}$ persist after discontinuation of the study medication.

Has been changed to:

Section 10.6.1 Liver function tests and evaluation of PDILI

The PDILI IMP discontinuation criteria for this study are provided in Section 10.6.1.2, with the accompanying required follow-up investigation and monitoring detailed below. All PDILI events must be reported as an AE and reported to the study site and sponsor within 24 hours of learning of their occurrence. Any PDILI event that meets the criterion for potential Hy's Law must be

reported as an AE of special interest (see Section 10.3), and, if applicable, also reported as an SAE (see Section 10.2).

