### **3.8 Coding dictionaries**

Medical history and AEs will be coded using the Medical Dictionary for Regulatory Activities (MedDRA® v16.1). Medications will be coded using the World Health Organization Drug Dictionary (WHODD SEP/2013). Medical procedures will not be coded.

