  - Incidence of TEAEs related to Potentially Drug Induced Liver Injury (PDILI) (defined in Appendix Section 12.3)
  - Incidence of pediatric growth-, neurodevelopment-, behavior-, and endocrine-related TEAEs (defined by manual medical review)
  - Incidence of non-serious TEAEs by relationship to LCM
  - Incidence of fatal TEAEs by relationship to LCM
  - Incidence of non-serious TEAEs occurring in at least 5% of subjects
  - Incidence of non-serious TEAEs occurring in at least 5% of subjects by relationship to LCM
  - Incidence of drug-related TEAEs by seriousness
  - Incidence of other significant TEAEs (defined in Appendix 12.2)

The following summaries of AEs will also be repeated by weight band and enrollment group using the levels defined in Sections 3.2.10 and 3.2.12 respectively.

- Incidence of TEAEs
- Incidence of serious AEs
- Incidence of serious TEAEs
- Incidence of TEAEs leading to discontinuation from the study
- Incidence of non-serious TEAEs occurring in at least 5% of subjects
- Incidence of drug-related TEAEs by seriousness
- Incidence of other significant TEAEs (defined in Appendix 12.2)

The following summaries of AEs will be presented for the 3-month time intervals (as defined in Section 3.2.5) of:  $\leq 3$  months,  $>3$  to  $\leq 6$  months,  $>6$  to  $\leq 9$  months,  $>9$  to  $\leq 12$  months,  $>12$  to  $\leq 15$  months,  $>15$  to  $\leq 18$  months,  $>18$  to  $\leq 21$  months,  $>21$  to  $\leq 24$  months, and  $\geq 24$  months:

- Incidence of all TEAEs with onset during the Treatment Period
- Incidence of all serious AEs with onset during the Treatment Period

- Incidence of all serious TEAEs with onset during the Treatment Period
- Incidence of all TEAEs leading to discontinuation from the study with onset during the Treatment Period
- Incidence of other significant TEAEs with onset during the Treatment Period (defined in Appendix 12.2)

In addition, summaries for the incidence of TEAEs overall, incidence of serious AEs, incidence of serious TEAEs, incidence of TEAEs leading to discontinuation, incidence of other significant TEAEs, TEAEs related to PDILI, and pediatric growth-, neurodevelopment-, behavior-, and endocrine-related TEAEs will be repeated presenting the site and subject number of all those subjects experiencing each TEAE as well as in subject data listings.

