**12.3 List of AEs for Potentially Drug Induced Liver Injury (PDILI)**

The following MedDRA PTs are defined as AEs for Potentially Drug Induced Liver Injury:

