**Table 12–4: AEs for PDILI**

MedDRA Preferred Term for PDILI
Acute hepatic failure
Alanine aminotransferase increased
Allergic hepatitis
Aspartate aminotransferase increased
Asterixis
Blood bilirubin abnormal
Blood bilirubin increased
Cholestasis
Cholestatic liver injury
Cholestatic pruritus

Chronic hepatitis
Coma hepatic
Cryptogenic cirrhosis
Drug-induced liver injury
Hepatic cirrhosis
Hepatic encephalopathy
Hepatic failure
Hepatic infiltration eosinophilic
Hepatic necrosis
Hepatic steatosis
Hepatitis
Hepatitis acute
Hepatitis cholestatic
Hepatitis chronic active
Hepatitis chronic persistent
Hepatitis fulminant
Hepatitis toxic
Hepatobiliary disease
Hepatocellular foamy cell syndrome
Hepatocellular injury
Hepatotoxicity
Hyperbilirubinaemia
Icterus index increased
Jaundice
Jaundice cholestatic

Jaundice hepatocellular
Liver disorder
Liver injury
Mixed liver injury
Non-alcoholic steatohepatitis
Ocular icterus
Subacute hepatic failure

PUBLIC COPY  
This document cannot be used to support any marketing authorization application and any extensions or variations thereof.

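### The PDILI adverse event table is built from a closed 42-term list with no term for a combined transaminase, liver enzyme or liver function test elevation, so a PDILI event coded that way would be left out of it

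*Protocol*

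**What the plan says.** Protocol Section 10.6.1, in its current text, states: "All PDILI events must be reported as an AE". It allows 24 hours for passing the report to the site and the sponsor. Section 6.3.1 and Table 10–3 define PDILI by ALT or AST thresholds, with bilirubin or symptoms as further conditions in some rows.

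On the wording of AEs, Protocol Section 10.1.3 says that "the investigator should use the overall diagnosis or syndrome using standard medical terminology, rather than recording individual symptoms or signs". SAP Section 3.8 says that "Medical history and AEs will be coded using the Medical Dictionary for Regulatory Activities", version 16.1.

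SAP Section 8.2 plans an incidence table of PDILI-related TEAEs and repeats it with site and subject numbers. It refers to Section 12.3 for the definition, which reads: "The following MedDRA PTs are defined as AEs for Potentially Drug Induced Liver Injury". Table 12–4 then lists the terms. The transaminase entries are "Alanine aminotransferase increased" and "Aspartate aminotransferase increased".

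Separately, SAP Section 8.3 checks the protocol PDILI criteria at all laboratory assessments and counts the subjects who meet them.

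**The concern.** The protocol makes every PDILI event an AE. The SAP recognises such an AE as PDILI-related only if its preferred term is on a fixed list. Section 8.2 gives no medical review, laboratory link or similar-terms rule for this table, although the next item in the same list, on growth, neurodevelopment, behavior and endocrine events, is defined by manual medical review.

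ALT and AST can rise together, and an investigator may report that as one finding. If it is coded to a term for raised transaminases, raised liver enzymes or abnormal liver function tests, the list does not pick it up. Two children with the same laboratory picture could be treated differently because of how the event was worded. A reader of the clinical study report would reasonably take the table as the full set of PDILI adverse events.

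**Working it through.** The plan gives no figure to reproduce. The check compares the event definition, the selection rule and the list.

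**1. What a PDILI event is.** The protocol criteria (Section 6.3.1, Table 10–3) are:

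- ALT or AST at least 5×ULN;
- ALT or AST at least 3×ULN with total bilirubin at least 2×ULN;
- ALT or AST at least 3×ULN with symptoms of hepatitis or hypersensitivity;
- ALT or AST at least 3×ULN (and at least 2× Baseline) but below 5×ULN, with bilirubin below 2×ULN and no symptoms.

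A transaminase rise is common to all four.

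**2. What the list can capture.** A text search of SAP Table 12–4 gives:

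| Search | Matching terms |
|---|---|
| All terms | 42 |
| aminotransferase | 2 (ALT increased, AST increased) |
| transaminase | 0 |
| enzyme | 0 |
| function | 0 |
| test | 0 |
| injury | 5 (including drug-induced liver injury, liver injury and hepatocellular injury) |

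So 2 of 42 terms name a transaminase, each a single enzyme, and 0 of 42 name a combined transaminase, enzyme or function-test abnormality. These are counts of terms, not of events.

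**3. Whether combined wording is foreseeable.** The protocol uses such wording itself. Section 10.6.1 has liver function tests in its heading and refers collectively to abnormal hepatic laboratory values, and Table 10–4 speaks of transaminase elevation. The report is due within 24 hours of learning of the event, while the tests for another cause come afterwards. The wording may therefore describe laboratory findings before there is a diagnosis.

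**4. Effect on the table.** Let N be the number of PDILI events reported as AEs and m the number whose only coded term is a combined one. The table shows at most N − m of them. The fraction missed through this gap is m/N, which can lie anywhere from 0 to 1. The documents give neither N nor m.

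**5. What else shows these events.** In SAP Section 8.3, the laboratory PDILI summary and the Baseline-to-maximum shift table (with a category of at least 3×ULN) work from results, not AE terms. The general TEAE tables in SAP Section 8.2, including the version with site and subject numbers, and the AE listings carry the event under whatever term it received.

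**The case against.** The strongest reply is that Section 10.1.3 points away from combined laboratory terms. Section 10.1.1 treats an abnormal laboratory finding as a sign, and Section 10.1.3 asks for a diagnosis in place of signs. An investigator who follows it would write drug-induced liver injury, hepatitis, hepatotoxicity or liver disorder, all of which are listed. One without a diagnosis might follow the protocol's ALT or AST wording, which matches the two enzyme terms. This stands as a reason why many events would be captured. It does not close the gap, because nothing in either document requires those wordings.

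A second reply is that the argument depends on dictionary content and coding practice that the documents do not give. This is fair, and it is why the conclusion is conditional: an event coded outside the list is not selected. Frequency is left open.

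A third reply is that the table was never a count of protocol-defined PDILI. It includes terms such as asterixis and hepatic steatosis, and it accepts an ALT increase of any size; the count against the criteria is in SAP Section 8.3. This is also right. Disagreement between the two displays is not in itself an error. But the SAP labels the table as PDILI-related TEAEs, and SAP Amendment 3 (Change #39) added the ALT and AST terms. That accepts that laboratory-type terms belong on the list.

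A reader might go further and infer that most or typical PDILI events will be missing, or that a liver signal would be lost to the report. The documents support neither: the share missed is unknown, and the affected children remain visible in the displays named in step 5.

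**Conclusion.** The point holds as a limited gap in one pair of safety displays. As the SAP is written, an event that meets the protocol PDILI criteria, and must be reported as an AE, can be absent from the PDILI TEAE table and its subject-number version because of its coded term alone.

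Its size in events cannot be given, and any percentage would be a guess. The only assumption is that at least one such event is coded to a combined term and to no listed term. If none is, these displays lose nothing through this gap.

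The three primary safety variables do not use Table 12–4, and Protocol Section 12.3 does not ask for a PDILI TEAE table. The change is still worth making: long-term safety is the primary objective, the table will be read as complete, and the remedy is cheap.

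**What to change.** In SAP Section 12.3, add to Table 12–4 the preferred terms, as they stand in the MedDRA version used for coding, for combined transaminase, hepatic enzyme and liver function test elevation or abnormality.

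In SAP Section 8.2, define PDILI TEAEs as the Table 12–4 terms plus any TEAE reported for an episode in which the subject meets the protocol PDILI criteria as identified by the SAP Section 8.3 check, whatever its preferred term. State how an AE is matched to an episode, and settle the matches before database lock.

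Do not tie the link to the eCRF pages for the work-up in Protocol Section 10.6.1.3. That work-up applies where IMP causation is a reasonable possibility, and Table 10–3 does not require testing for asymptomatic rises from 3× to below 5×ULN. Such a link would itself miss some PDILI events.

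The cost is a few added terms and one linking step on AE and laboratory data already collected. Nothing changes in the conduct of the study.

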10.6.1.1 Consultation with Medical Monitor and local hepatologist

Potential drug-induced liver injury events require notification of the Medical Monitor within 24 hours (eg, by laboratory alert), and the subject must be discussed with the Medical Monitor as soon as possible. If required, the subject must also be discussed with the local hepatologist. The local hepatologist is the expert usually consulted by the treating physician for assessment and management of potential hepatic disease. This would usually be a hepatologist, but may be a gastroenterologist. If determined necessary, this discussion should be followed by a full hepatology assessment (see Section 10.6.1.3) and SAE report (if applicable).

10.6.1.2 Immediate action: determination of IMP discontinuation

All PDILI events require immediate action, testing, and monitoring.

The immediate action is dependent on the laboratory values and symptoms of hepatitis or hypersensitivity and ranges from continuation of IMP (followed by immediate investigation) to immediate and permanent discontinuation (see Section 6.3.1 and Table 10-3 for details).

When IMP is discontinued, all concomitant medications and herbal supplements that are not medically necessary should also be discontinued. The investigator should also consider dose reduction for medically necessary concomitant medication and consider changing any medically required concomitant medication known to be hepatotoxic to a suitable alternative.

10.6.1.3 Testing: identification/exclusion of alternative etiology

The measurements and additional information required for the assessment of PDILI events when there is a reasonable possibility that they may have been caused by the IMP are detailed in Table 10-4 (laboratory measurements) and Table 10-5 (additional information). Results of the laboratory measurements and information collected are to be submitted to the sponsor on the corresponding eCRF. If the medical history of the subject indicates a requirement for other assessments not included below, these additional assessments should be completed and submitted, as applicable.

All blood samples should be stored, if possible. If tests are done locally for more rapid results, a concurrent sample must also be sent to the central laboratory.

The following measurements are to be assessed:

Table 10-4: PDILI laboratory measurements

Virology-related	Hepatitis A IgM antibody
	HBsAg
	Hepatitis E IgM antibody
	HBcAb-IgM
	Hepatitis C RNA
	Cytomegalovirus IgM antibody
	Epstein-Barr viral capsid antigen IgM antibody (if unavailable, obtain heterophile antibody or monospot testing)
Immunology	Anti-nuclear antibody (qualitative and quantitative)

Table 10-4: PDILI laboratory measurements

	Anti-smooth muscle antibody (qualitative and quantitative)
	Type 1 anti-liver kidney microsomal antibodies (qualitative and quantitative)
Hematology	Eosinophil count
Urinalysis	Toxicology screen
Chemistry	Amylase
	If total bilirubin $\geq 1.5 \times \text{ULN}$, obtain fractionated bilirubin to obtain % direct bilirubin
	Serum CPK and LDH to evaluate possible muscle injury causing transaminase elevation
Additional	Prothrombin time/INR ^a
	Serum pregnancy test in women of childbearing potential
	PK sample

CPK=creatine phosphokinase; HBcAb-IgM=hepatitis B core antibody-IgM; HBsAg=hepatitis B surface antigen; IgM=immunoglobulin M; INR=international normalized ratio; LDH=lactate dehydrogenase; PDILI=potential drug-induced liver injury; PK=pharmacokinetic; RNA=ribonucleic acid; ULN=upper limit of normal

^a Measured only for subjects with ALT $> 8 \times \text{ULN}$, elevations in total bilirubin, and symptoms of hepatitis or hypersensitivity. Hepatitis symptoms include fatigue, nausea, vomiting, and right upper quadrant pain or tenderness; hypersensitivity symptoms include eosinophilia ($> 5\%$), rash, and fever (without clear alternative cause).

The following additional information is to be collected:

Table 10-5: PDILI information to be collected

New or updated information
Concomitant prescription and over-the-counter medications (eg, acetaminophen, herbal remedies, vitamins); dosages and dates should be included.
Pertinent medical history, including the following: 
 • History of liver disease (eg, autoimmune hepatitis, nonalcoholic steatohepatitis or other “fatty liver disease”) • Adverse reactions to drugs • Allergies • Relevant family history or inheritable disorders (eg, Gilbert’s syndrome, alpha-1 antitrypsin deficiency) • Recent travel • Progression of malignancy involving the liver (Note: Metastatic disease to the liver, by itself, should not be used as an explanation for significant AST and/or ALT elevations.)
The appearance or worsening of clinical symptoms of hepatitis or hypersensitivity (eg, fatigue, nausea, vomiting, right upper quadrant pain or tenderness, decreased appetite, abdominal pain, jaundice, fever, or rash)
Recent clinically significant hypotension or hypoxemia with compromised cardiopulmonary function
Alcohol and illicit drug use

Table 10-5: PDILI information to be collected

New or updated information
Results of liver imaging or liver biopsy, if done
Results of any specialist or hepatology consult, if done
Any postmortem/pathology reports

ALT=alanine aminotransferase; AST=aspartate aminotransferase; PDILI=potential drug-induced liver injury

10.6.1.4 Follow-up evaluation

Potential drug-induced liver injury events require follow-up monitoring as described in [Table 10-3](#). Monitoring should continue until liver chemistry values normalize, stabilize, or return to Baseline. Determination of stabilization is at the discretion of the investigator in consultation with the hepatologist (as applicable) and UCB responsible physician, as needed.

Change #15

Section 15 REFERENCES

The following reference has been removed:

Dichek B. Epilepsy: an ancient ailment that still eludes a cure. Scrip Magazine. 1999;Feb:9 11.

And the following references have been added:

16.3 Protocol Amendment 3

Rationale for the amendment

The primary purpose of this nonsubstantial amendment is to clarify when both the Safety Follow-Up Visit and the Safety Follow-Up Telephone Contact are not required. In addition, language specifying the use of local laboratories in exceptional circumstances and applicable study conduct modifications due to the COVID-19 pandemic have been added.

Furthermore, minor administrative changes have been made, including the update of the study team.

Modifications and changes

Global changes

- The name and contact information for the Sponsor Study Physician, Clinical Project Manager, and Clinical Trial Biostatistician were updated.
- Text updated to clarify the Safety Follow-Up Visit and the Safety Follow-Up Telephone Contact.
- Text added to clarify study conduct due the COVID-19 pandemic.
- Study variables were reorganized to clarify categorization of primary, secondary, and other.
- Text added to clarify the use of local laboratories in exceptional circumstances.
- Assessments added for PDILI laboratory measurements.
- Minor editorial changes have been made throughout the protocol.

Specific changes

Change #1

STUDY CONTACT INFORMATION

Sponsor Study Physician

Name:	██████████
Address:	UCB BIOSCIENCES, Inc. [name] UNITED STATES
Phone:	██████████
Fax:	██████████

Clinical Project Manager

Name:	██████████
Address:	UCB BIOSCIENCES GmbH [name] GERMANY
Phone:	██████████
Fax:	██████████

Clinical Trial Biostatistician

Name:	██████████
Address:	UCB BIOSCIENCES, Inc. [name] UNITED STATES
Phone:	██████████
Fax:	██████████

Has been changed to:

Sponsor Study Physician

Name:	██████████
Address:	UCB BIOSCIENCES GmbH [name] GERMANY
Phone:	██████████
Email:	██████████

Clinical Project Manager

Name:	██████████
Address:	UCB Biopharma SRL [name] UNITED KINGDOM
Phone:	██████████

Email:	[REDACTED]
--------	------------

Clinical Trial Biostatistician

Name:	[REDACTED]
Address:	UCB BIOSCIENCES, Inc. [name] UNITED STATES
Phone:	[REDACTED]
Email:	[REDACTED]

Change #2

Section 1 SUMMARY, paragraph 5:

During the Treatment Period, study visits are scheduled at Weeks 0, 4, 8, 12, 20, 28, 36, 44, 52, 60, 72, 84, and 96. Telephone contacts are scheduled at Weeks 2, 6, 10, 16, 24, 32, 40, 48, 56, 66, and 78. Subjects who withdraw from treatment during the study should taper off LCM if the following doses are achieved: LCM ≥ 3 mg/kg/day (oral solution) for subjects receiving LCM oral solution, or LCM ≥ 150 mg/day (tablet) for subjects taking tablets; lower doses will not require a taper. An Early Termination Visit must be completed for all subjects who prematurely discontinue from the study. Subjects who complete the study or withdraw prematurely from the study, and who discontinue use of LCM, should complete a Safety Follow-Up Visit 2 weeks (± 2 days) after the final dose of LCM. A Safety Follow-Up Telephone Contact will be made 30 days (-1/+3 days) after the final dose of LCM. At the completion of the study, investigators should discuss treatment options with the subject and/or their legal representative(s) to best manage the subject's epilepsy. Taper of LCM may not be required for some subjects who complete the study or withdraw from the study prematurely, depending on the treatment option selected by the investigator in consultation with the subject and/or legal representative(s).

Has been changed to:

During the Treatment Period, study visits are scheduled at Weeks 0, 4, 8, 12, 20, 28, 36, 44, 52, 60, 72, 84, and 96. Telephone contacts are scheduled at Weeks 2, 6, 10, 16, 24, 32, 40, 48, 56, 66, and 78. Subjects who withdraw from treatment during the study should taper off LCM if the following doses are achieved: LCM ≥ 3 mg/kg/day (oral solution) for subjects receiving LCM oral solution, or LCM ≥ 150 mg/day (tablet) for subjects taking tablets; lower doses will not require a taper. An Early Termination Visit must be completed for all subjects who prematurely discontinue from the study. Subjects who complete the study or withdraw prematurely from the study, and who discontinue use of LCM, should complete a Safety Follow-Up Visit 2 weeks (± 2 days) after the final dose of LCM. A Safety Follow-Up Telephone Contact will be made 30 days (-1/+3 days) after the final dose of LCM. The Safety Follow-Up Visit and the Safety Follow-Up Telephone Contact are not required for subjects who participate in EP0151 or EP0152. At the completion of the study, investigators should discuss treatment options with the

subject and/or their legal representative(s) to best manage the subject's epilepsy. Taper of LCM may not be required for some subjects who complete the study or withdraw from the study prematurely, depending on the treatment option selected by the investigator in consultation with the subject and/or legal representative(s).

Change #3

Section 4, STUDY VARIABLES, all subsections (4.1, 4.2, 4.3, and 4.4):

